13. CONFIDENTIALITY

The Investigator will take the following precautionary measures to protect the privacy and

FMT in UC-associated Pouchitis

Version 3.0, date finalized 06/26/2017

confidentiality of the subject's research and/or medical records.

- The donated blood and mucosal tissue collected through this study will be given a code (or number) that is not derived from or related to information about the individual and is not otherwise capable of being translated to identify an individual.
- Access to medical and research records will be limited to clinical and research personnel assigned to data collection and monitoring for this study. Only those medical records pertaining to the study will be reviewed.
- Research records will be de-identified and maintained in a secured location.
- Dates recorded on research records will be limited to those essential to completion of the study.
- No individual identifiers will be used in any publications or reports resulting from the study.

PI and authorized study staff will have access to a secure file containing linkages of biological samples to subject identities.

A copy of the consent form will be included in the subject's medical research record.

13.1 Compliance Statement

The study will be conducted in accordance with the protocol, Good Clinical Practices, the relevant ICH guidelines, the applicable regulatory requirements, and the ethical principles that have their origins in the Declaration of Helsinki. As required by United States Food and Drug Administration (FDA) Code of Federal Regulations (CFR) (21 CFR 56) and the Declaration of Helsinki, the study protocol, amendments, and Informed Consent form will be reviewed and approved, according to 21 CFR §50 and §56, respectively, by IRB.

13.2 Subject Information and Consent

The study will be explained to each subject, they will have the opportunity to read the informed consent document, ask questions and have their questions answered to their satisfaction. Alternatives to participation in this study will be explained. Patients will be informed that their participation in this study is voluntary and that their decision regarding participation will not affect their ability to receive care. Prior to any study procedures, the IRB approved Informed Consent form will be signed by each subject. A copy of the consent form will be given to each patient approached for participation in the study.

The Emory University IRB will review the written Informed Consent Form. These documents will meet requirements for subject information, as outlined in FDA regulations (21 CFR 50), ICH Guideline E6, and the Declaration of Helsinki.

FMT in UC-associated Pouchitis

Version 3.0, date finalized 06/26/2017

14. COSTS

14.1 Donor Activities Related Costs

The cost of all donor serology and stool testing will be covered by the sponsor. Fecal sample preparation will also be covered by the sponsor.

14.2. Research Participant Activities Related Costs

All physical exams will be covered by principal investigator and/or sub-investigator effort. Waist to hip circumference will be taken during the physical exam for each visit, therefore, they will also be considered as physician effort. Urine pregnancy kits used during for screening WOCBP will be covered by sponsor funds. All associated labs and specimen processing (i.e. stool collection, plasma collection, urine collection, and CBCs with differential and platelet count will also be covered. The flexible sigmoidoscopy with moderate sedation will be covered by the sponsor. Eligible research participants who enroll in the study will not be paid for their participation.

APPENDIX 1: MODIFIED POUCH DISEASE ACTIVITY INDEX (MPDAI)

15

Appendix 1: Modified PDAI

Table 1.
The Pouchitis Disease Activity Index^a

Criteria	Score
Clinical	
Stool frequency	
Usual postoperative stool frequency	0
1-2 stools/day :- postoperative usual	1
3 or more stools/day :- postoperative usual	2
Rectal bleeding	
None or rare	0
Present daily	1
Focal urgency or abdominal cramps	
None	0
Occasional	1
Usual	2
Fever (temperature >= 37.8° C)	
Absent	0
Present	1
Endoscopic inflammation	
Edema	1
Granularity	1
Friability	1
Loss of vascular pattern	1
Mucous exudates	1
Ulceration	1
Acute histologic inflammation	
Polymorphic nuclear leukocyte infiltration	
Mild	1
Moderate + crypt abscess	2
Severe + crypt abscess	3
Ulceration per low-power field (mean)	
>25%	1
25-50%	2
>50%	3

FMT in UC-associated Pouchitis
v.date 10.30.2015

APPENDIX 2: FECAL DONOR QUESTIONNAIRE

16

Appendix 2: Fecal donor questionnaire

Fecal Transplant Donor History Questionnaire

Donor Name _____

Patient Name _____

Date _____

Please Circle Yes or No

*Answers will be kept strictly confidential, please answer honestly

Are you

- | | | |
|---|-----|----|
| 1. Feeling healthy and well today? | Yes | No |
| 2. Currently taking any medication for infection? | Yes | No |

Have you

- | | | |
|---|-----|----|
| 3. Taken any antibiotics within the past 3 months? | Yes | No |
| 4. Had any fevers, vomiting, diarrhea or other symptoms of infection within the past 4 weeks? | Yes | No |

In the past 8 weeks have you

- | | | |
|--|-----|----|
| 5. Had any vaccinations or other shots? | Yes | No |
| 6. Had contact with someone who has had a recent Smallpox vaccine? | Yes | No |

In the past 12 months have you

- | | | |
|-----------------------------|-----|----|
| 7. Had a blood transfusion? | Yes | No |
|-----------------------------|-----|----|

FMT in UC-associated Pouchitis
v.date 10.30.2015

8. Had a transplant (organ, tissue, bone marrow)? Yes No
9. Had a skin or bone graft? Yes No
10. Come into contact with someone else's blood? Yes No
11. Had an accidental needle stick? Yes No
12. Had sexual contact with anyone who has HIV/AIDS? Yes No
13. Had sexual contact with a prostitute or anyone else who takes money or drugs as payment for sex? Yes No
14. Had sexual contact with anyone who has ever used needles to take drugs or steroids, or anything NOT prescribed by their doctor? Yes No
15. Had sexual contact with anyone who has hemophilia or has used clotting factor concentrates? Yes No
16. *Female donors:* Had sexual contact with a male who has ever had sexual contact with another male (male donors circle "I am male")? Yes No I am male
17. Had sexual contact with a person who has hepatitis? Yes No
18. Lived with a person who has hepatitis? Yes No
19. Had a tattoo? Yes No
20. Had an ear or body piercing? Yes No
21. Been treated for syphilis or gonorrhea? Yes No
22. Been in lockup, jail or prison for >72 hours? Yes No
- In the past three years have you**
23. Been outside the United States or Canada? Yes No
List location/time spent: _____
- From 1980 through 1996**
24. Did you spend time that adds up to three (3) months FMT in UC-associated Pouchitis v.date 10.30.2015 Yes No

or more in the United Kingdom?

25. Were you a member of the U.S. military, a civilian military employee or a dependent member of the U.S. military? Yes No

From 1980 to the present, did you

26. Spend time that adds up to five (5) or more years in Europe? Yes No

27. Receive a blood transfusion in the United Kingdom or France? Yes No

From 1977 to the present, have you

28. Received money, drugs, or other payment for sex? Yes No

29. *Male donors:* had sexual contact with another male, even once (female donors circle "I am female")? Yes No I am female

Have you EVER

30. tested positive for HIV/AIDS virus? Yes No

31. used needles to take drugs or steroids or anything NOT prescribed by your doctor? Yes No

32. used clotting factor concentrates? Yes No

33. had viral hepatitis? Yes No

34. had any type of cancer (including leukemia)? Yes No

35. had sexual contact with anyone who was born or lived in Africa? Yes No

36. been in Africa? Yes No

37. had sex for drugs or money? Yes No

38. had any of the following gastrointestinal diseases or other medical problems?

- Irritable bowel syndrome? Yes No
- Crohn's disease? Yes No
- Ulcerative Colitis? Yes No
- Chronic diarrhea? Yes No

FMT in UC-associated Pouchitis
v.date 10.30.2015

- Gastrointestinal cancers? Yes No
 - Celiac disease? Yes No
 - Morbid obesity? Yes No
 - Metabolic syndrome Yes No
 - Colon polyps Yes No
 - Chronic fatigue Yes No
 - Suppressed immune system? Yes No
 - Allergic disorder? Yes No
39. received a dura mater (brain covering) graft? Yes No
40. received growth hormone made from human Pituitary glands? Yes No
41. Have any of your relatives had Creutzfeldt-Jakob disease? Yes No

General Medical History

42. Have you had any gastrointestinal surgery (for example: appendectomy, gallbladder surgery, gastric bypass) Yes No
If yes, please list: _____
43. Do you have any autoimmune diseases (for example: Rheumatoid arthritis, Multiple Sclerosis, Lupus) Yes No
If yes, please list: _____
44. Have you ever been treated for any cancer or malignancy? Yes No
45. What is your weight? _____ What is your height? _____

FMT in UC-associated Pouchitis
v.date 10.30.2015

**APPENDIX 3:
MEDWATCH FORM**

Please see attached US Food and Drug Administration Document entitled FDA 3500.

**APPENDIX 4:
QUALITY OF LIFE SURVEY TOOLS**

21

Appendix 4: Quality of Life Survey tools

Cleveland Global Quality of Life Score	
Please rate the following on a scale of 0-10 (where 10 is the best)	
Current Quality of Life	
Current Quality of Health	
Current Energy Level	

FMT in UC-associated Pouchitis
v.date 10.30.2015

Short Quality of Life Questionnaire for Inflammatory Bowel Disease

Name _____ Date _____

This questionnaire is designed to find out how you have been feeling during the last 2 weeks. You will be asked about symptoms you have been having as a result of your inflammatory bowel disease, the way you have been feeling in general, and how your mood has been. Please circle the number of your choice below each question.

1. How often has the feeling of fatigue or being tired and worn out been a problem for you during the past 2 weeks?
 1. All of the time
 2. Most of the time
 3. A good bit of the time
 4. Some of the time
 5. A little of the time
 6. Hardly any of the time
 7. None of the time

2. How often during the last 2 weeks have you delayed or canceled a social engagement because of your bowel problem?
 1. All of the time
 2. Most of the time
 3. A good bit of the time
 4. Some of the time
 5. A little of the time
 6. Hardly any of the time
 7. None of the time

3. As a result of your bowel problems, how much difficulty did you experience doing leisure or sports activities you would liked to have done during the past 2 weeks?
 1. A great deal of difficulty; activities made impossible
 2. A lot of difficulty
 3. A fair bit of difficulty
 4. Some difficulty
 5. A little difficulty
 6. Hardly any difficulty
 7. No difficulty; the bowel problem did not limit sports or leisure activities

4. How often during the past 2 weeks have you been troubled by pain in the abdomen?
 1. All of the time
 2. Most of the time
 3. A good bit of the time
 4. Some of the time
 5. A little of the time
 6. Hardly any of the time
 7. None of the time

Irvine, E. J., et al. The short inflammatory bowel disease questionnaire: A quality of life instrument for community physicians managing inflammatory bowel disease. Am J Gastroenterology. 1996; 91(8):1571-8 Aug.

FMT in UC-associated Pouchitis
v.date 10.30.2015

5. How often during the past 2 weeks have you felt depressed or discouraged?
1. All of the time
 2. Most of the time
 3. A good bit of the time
 4. Some of the time
 5. A little of the time
 6. Hardly any of the time
 7. None of the time
6. Overall, in the past 2 weeks, how much of a problem have you had with passing large amounts of gas?
1. A major problem
 2. A big problem
 3. A significant problem
 4. Some problem
 5. A little trouble
 6. Hardly any trouble
 7. No trouble
7. Overall, in the past 2 weeks, how much of a problem have you had maintaining or getting to the weight you would like to be?
1. A major problem
 2. A big problem
 3. A significant problem
 4. Some problem
 5. A little trouble
 6. Hardly any trouble
 7. No trouble
8. How often during the past 2 weeks have you felt relaxed and free of tension?
1. All of the time
 2. Most of the time
 3. A good bit of the time
 4. Some of the time
 5. A little of the time
 6. Hardly any of the time
 7. None of the time
9. How much of the time during the past 2 weeks have you been troubled by a feeling of having to go to the bathroom even though your bowels were empty?
1. All of the time
 2. Most of the time
 3. A good bit of the time
 4. Some of the time
 5. A little of the time
 6. Hardly any of the time
 7. None of the time
10. How often during the past 2 weeks have you felt angry as a result of your bowel problem?
1. All of the time
 2. Most of the time
 3. A good bit of the time
 4. Some of the time
 5. A little of the time
 6. Hardly any of the time
 7. None of the time

Irvine, E. J., et al. The short inflammatory bowel disease questionnaire: A quality of life instrument for community physicians managing inflammatory bowel disease. Am J Gastroenterology. 1996; 91(8):1571-8 Aug.

FMT in UC-associated Pouchitis
v.date 10.30.2015

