1. SPECIFIC AIMS

The aims of this study are: 1) to determine the utility of fecal microbiota transplantation (FMT) in the treatment of patients with ulcerative colitis (UC) associated chronic antibiotic-dependent pouchitis (CADP) and chronic antibiotic refractory pouchitis (CARP) and 2) to study the changes in the microbial environment in patients with pouchitis (pre- and post-treatment) and 3) to assess the impact of therapy on the patient's perceived quality of life.

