9. DATA ANALYSIS

Patients will be identified by physicians on this protocol in The Emory Clinic or Emory

FMT in UC-associated Pouchitis

Version 3.0, date finalized 06/26/2017

University Hospital. Patients will be consented using an IRB approved informed consent and undergo the procedure on their follow up visit.

Since this is a pilot study, no formal power calculation is provided. Descriptive statistics and ANOVA will be used to detect differences between groups. One-sample t-test or Wilcoxon's signed rank-tests will be used to see if there were any significant changes in PDAI and QOL scores before and after transplant. A Simon's two stage design will be used to decide whether to enroll more patients in the future.

Data relating to laboratory results will be obtained through the EMR computerized patient information systems EML microbiological reports. A dataset will be created in a secure file, with access given only to authorized study staff.

A list of possible cases that have been reviewed for inclusion will be secured by study staff. This list will contain subject name, birth date, medical record number, and the number of the corresponding data abstraction sheet. Such a list will be maintained so as not to duplicate the abstraction of a single subject. Once the data from all included subjects is entered into a database, the list of identifiable patient information will be destroyed.

Data analysis will be performed with Microsoft Excel, SAS Institute software, and SPSS software.

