10. ENDPOINTS

The primary endpoint of this study will be resolution of clinical pouchitis symptoms using the clinical component of the modified pouchitis disease activity index without relapse for 3 months. Secondary endpoints include 16S ribosomal gene sequencing and metabolomic profiles that are more favorable (as defined by the donor microbiota). An additional secondary endpoint will be improvement of quality of life as determined by QOL questionnaires.

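### Item 8 of the printed short IBD questionnaire runs opposite to the other nine and has no recoding rule, so totalling the circled numbers would mis-score it; the QOL baseline visit is also stated two ways

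*Combined protocol and SAP*

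**What the plan says.** Quality of life is the third aim in Section 1 ("to assess the impact of therapy on the patient's perceived quality of life"), and Section 10 lists as a secondary endpoint "improvement of quality of life as determined by QOL questionnaires". Section 9 plans one-sample t-tests or Wilcoxon signed-rank tests "to see if there were any significant changes in PDAI and QOL scores before and after transplant". Two instruments are named in Section 3.7 and printed in Appendix 4: the short IBD questionnaire and the Cleveland Global Quality of Life score.

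Each of the ten items of the short IBD questionnaire has answers numbered 1 to 7, and the form tells the patient only to circle a number. Item 5 ("How often during the past 2 weeks have you felt depressed or discouraged") and item 10 ("How often during the past 2 weeks have you felt angry as a result of your bowel problem") use a frequency scale from 1, all of the time, to 7, none of the time. Item 8 ("How often during the past 2 weeks have you felt relaxed and free of tension") uses the same scale in the same order. Neither the form nor any protocol section says how a score is formed from the items.

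On timing, Section 3.7 has the surveys completed at enrollment, 4 weeks and 12 weeks. Table 2 in Section 3.6 ticks them at screening, 4 weeks and 3 months and leaves the enrollment cell blank.

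**The concern.** Feeling angry or depressed none of the time is good; feeling relaxed none of the time is bad. Item 8 therefore points the opposite way from the rest of the form. An analyst who follows the protocol as written has no instruction to reverse it. If the circled numbers are added up, a patient who becomes more relaxed loses points on that item, and the reported change in a stated secondary endpoint has the wrong size.

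The baseline conflict matters because the before/after test needs a single before value. The form states its own recall period: "This questionnaire is designed to find out how you have been feeling during the last 2 weeks". Section 3.6 b requires antibiotics and probiotics to be stopped at least 48 hours before the transplant. Footnote 2 of Table 2 makes special provision for screening and enrollment falling within 7 days of each other, which implies that they may lie further apart, and no maximum gap is given. The two visits can therefore describe different states of the same patient.

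**Working it through.** The documents state no questionnaire total, range or expected change, so there is no figure to reproduce. The check uses the printed answers only.

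**Direction of each item (Appendix 4).**
- Items 1, 2, 4, 5, 9 and 10: a negative state, with 7 = none of the time. 7 is best.
- Item 3: 7 = no difficulty. 7 is best.
- Items 6 and 7: 7 = no trouble. 7 is best.
- Item 8: a positive state, with 7 = none of the time. 7 is worst.

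Nine items run one way and one runs the other.

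**Error in one visit's total.** Let c be the number circled on item 8. Recoded to the direction of the other items it is 8 - c. Total as circled minus recoded total = c - (8 - c) = 2c - 8. This is -6 at c = 1, 0 at c = 4 and +6 at c = 7.

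**Extremes.**
- Best health: as circled 9 × 7 + 1 = 64; recoded 10 × 7 = 70.
- Worst health: as circled 9 × 1 + 7 = 16; recoded 10 × 1 = 10.

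**Error in a change.** A true gain of k points on item 8 counts as a loss of k, so that patient's change is too low by 2k. Since k is at most 6, the error is at most 12 points.

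**Size for a general improvement.** Let nine items gain d points each and item 8 gain f × d. The true change is (9 + f)d and the recorded change is (9 - f)d. The understatement is 2f/(9 + f):
- f = 1: recorded 8d against 10d, 20%.
- f = 0.5: recorded 8.5d against 9.5d, 10.5%.
- f = 0: 9d either way, 0%.

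For f from 0 to 1 the direction of the change is kept.

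**Effect on the test.** Write S for a patient's summed gain on the nine items and X for the true gain on item 8. The correct change is S + X; the change as circled is S - X.
- If X = aS in every patient, with the same a between 0 and 1 (1 excluded), the two changes are (1 + a)S and (1 - a)S. They differ only by a constant factor, so the t-test and the signed-rank test are both unchanged. This includes the case where item 8 does not move.
- Equal movement is not enough. Assume n = 11 (Section 6), X = 1 in every patient, and S with mean 9 and SD 13. Correct: t = (10/13) × √11 = 2.55, p = 0.029. As circled: t = (8/13) × √11 = 2.04, p = 0.069.
- The shift can also go the other way. Assume equal SDs and a common correlation r between item gains. In units of one item's variance, the variance of the correct change is 10 + 90r and of the change as circled 10 + 54r. The ratio of standardized effects, as circled to correct, is [(9 - f)/(9 + f)] × √[(10 + 90r)/(10 + 54r)]. At r = 0.3 the square root is √(37/26.2) = 1.188. With f = 1 the ratio is 0.8 × 1.188 = 0.951, weaker; with f = 0 it is 1.188, stronger.

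**Baseline visit.** Section 3.6 lists screening and enrollment as two of five separate visits. Table 2 keeps them apart on purpose: it ticks the Food Recall Questionnaire at enrollment, in agreement with Section 5, and the quality-of-life forms at screening. Footnote 2 concerns research samples, not questionnaires, so it does not resolve the conflict with Section 3.7. The documents give nothing from which to size its effect.

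**The case against.** The strongest reply is that Appendix 4 holds a patient-facing form, not a scoring manual, and that the form cites the instrument's source publication. A scoring rule may be given there and study staff may apply it. Part of this stands. A reader might infer that the quality-of-life results will be wrong; the documents do not support that, because nowhere do they say that the items are summed, let alone summed as circled. Nor can it be decided from them whether item 8 is a printing slip or a faithful copy meant to be recoded. But the protocol neither reproduces a scoring rule nor says that it will follow one, so the gap remains in either case.

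Four other stronger readings are tempting.
- *The whole quality-of-life endpoint is compromised.* It rests on two instruments. The three Cleveland ratings all run from 0 to 10 with 10 best, so that score is untouched.
- *The error costs the trial power.* Section 9 gives no power calculation, and the documents state no alpha, SD or expected effect. Any power figure would rest wholly on assumed values, and the effect can go in either direction.
- *Section 3.7 requires the surveys before endoscopy.* It places them only at enrollment; the wording there about documentation before endoscopy belongs to the symptom score. Since screening also precedes the transplant, the documents call for the two places to be reconciled but do not settle which visit to use.
- *Section 9 compares a full PDAI before transplant with a clinical-only score after it.* It uses the bare term PDAI, but Table 2 marks every follow-up score as clinical and Section 10 names the clinical component. No such comparison is ordered.

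**Conclusion.** The point holds and should be fixed, in a conditional form. That item 8 runs against the other nine, and that no recoding rule exists in the documents, can be read directly from them. Actual mis-scoring depends on the circled numbers being totalled without recoding. In that case each visit's total is wrong by up to 6 points either way, and a uniform gain is understated by 20%, falling to zero if item 8 does not move. The test is sure to be unaffected only if item 8 moves in the same proportion to the other items in every patient; otherwise the p-value can rise or fall. The damage is limited to one of two instruments behind a secondary endpoint in an 11-patient pilot. The primary endpoint is not touched.

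The baseline contradiction between Table 2 and Section 3.7 is also real. Its effect cannot be sized from the documents.

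**What to change.** 1. Check item 8 against the source form. Then either correct its printed response order in Appendix 4 (1 = none of the time, 7 = all of the time) or state in Section 9 that item 8 is scored as 8 minus the circled number before summing. Do not do both to the same form. Forms already completed on the printed version are recoded.
2. State in Section 9 that the total runs from 10 (worst) to 70 (best).
3. Reconcile Table 2 with Section 3.7 so that one visit, with the form completed before the transplant, is the quality-of-life baseline for all subjects. If enrollment is chosen, state how subjects surveyed only at screening are handled.

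The cost is one or two sentences in Section 9 or one reprinted item, plus one moved tick or one reworded sentence for the baseline. Item 8 answers already given can be recovered in full by recoding. The one downside is that, if enrollment becomes the baseline, anyone surveyed only at screening has no enrollment score, and the screening score must serve instead.
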